2.3 Treatment pooling and handling of pre-amendment 2 patients

Patients randomized prior to implementation of protocol amendment 2, dated 30-Jun-2015, were receiving a weight-based dose and were to be treated for 52 weeks. After consenting to protocol amendment 2, their treatment regimen was converted in a blinded manner via the Interactive Response Technology (IRT) system to a fixed-dose treatment regimen at their next scheduled visit. Patients on 3 mg/kg bimagrumab were converted in a blinded manner to 210 mg bimagrumab fixed dose and patients on 10 mg/kg bimagrumab were converted in a blinded manner to 700 mg bimagrumab.

Patients who had already completed Week 20 had their EOT (Week 24) assessments performed at their next scheduled visit after which they continued the study as per protocol amendment 2. Patients randomized prior to implementation of protocol amendment 2 may therefore have been treated for more than 24 weeks (more than 6 infusions).

Patients who entered the study prior to protocol amendment 2 will be pooled with fixed-dose patients as follows:

Table 2.1 Treatment pooling

Time of Entry into Study	Randomized	Analyzed
Prior to protocol amendment 2*	Placebo	Placebo
	Bimagrumab 3 mg/kg	Bimagrumab 210 mg
	Bimagrumab 10 mg/kg	Bimagrumab 700 mg

After protocol amendment 2	Placebo	Placebo
	Bimagrumab 70 mg	Bimagrumab 70 mg
	Bimagrumab 210 mg	Bimagrumab 210 mg
	Bimagrumab 700 mg	Bimagrumab 700 mg

*For patients who entered the study prior to protocol amendment 2 and potentially treated for more than 6 months (24 weeks).

Subsequently, for the pre-amendment 2 patients potentially treated for more than 24 weeks (more than 6 infusions), the treatment epoch, as used for analysis purposes, is defined as the first 24 weeks of treatment only i.e. start of the first infusion of study drug (Day 1) to last infusion of study drug cut-off at Week 20 + 4 weeks. Implying a total of 6 infusions within the defined 24-week treatment epoch.

Taking the aforementioned defined 24-week treatment epoch into account, the same conventions for defining treatment-emergent events (as well as assessments with clinically notable criteria defined, such as laboratory assessments, vital signs, electrocardiogram etc.) and for identifying concomitant medications will apply for all patients regardless of whether they were randomized pre- or post-amendment 2:

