- Treatment-emergent: AEs will be deemed treatment-emergent if the date of onset or worsening of the AE is on or after the start of the first infusion of study drug (Day 1) until the last infusion of study drug (expected per protocol at Week 20) + 56 days.
- Concomitant definition: Concomitant medications defined as any medication which started or stopped on or after the start of the first infusion of study drug (Day 1) up to the last infusion of study drug (expected per protocol at Week 20) + 56 days or is ongoing.

In addition, analysis and presentation of patients' data beyond Week 24 (end of defined treatment epoch) will be handled as follows:

- Study drug administration data (Actual exposure to study drug [days] and exposure to study drug [days], cut-off): For pre-amendment 2 patients potentially treated for more than 24 weeks (more than 6 infusions), study drug administration data after Week 20 will be recorded in the Dose administration record – infusion electronic case report form (eCRF). For both pre- and post-amendment 2 patients, exposure to study drug will therefore be summarized by actual exposure days based on overall treatment duration, regardless of the defined 24-week treatment epoch (i.e. disregarding the cut-off at 6 months [24 weeks] treatment) and days exposed within the defined 24-week treatment epoch:
 - Actual exposure: ([Actual last infusion date + 56 days] – First infusion date) + 1 day.
 - Exposure, cut-off: ([Last infusion date, within the 24-week defined treatment epoch + 56 days] – First infusion date) + 1 day.
- DXA assessment data recorded after Week 24, for example at Week 36, Week 48 or Week 52, in the Body composition –DXA eCRF will be listed in by-patient data listings only. Subsequently, if treated for more than 6 months, the defined treatment epoch will comprise the first 24 weeks of treatment only as described above. The change in DXA assessments will be analyzed based on the first 24 weeks of treatment only as applied for all patients in the study, whether they were randomized pre- or post-amendment 2.

The same conventions and definitions will be applied whether the patient completes treatment or prematurely discontinues treatment or study. Similarly, regardless if the analysis is performed at the time of the primary or final update analysis.

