2.9.1 Study drug administration

The number of infusions received (to a maximum of 6 infusions per protocol amendment 2), will be presented using descriptive statistics by treatment group and across all four treatment groups combined. The number (n) and percentage (%) of infusions received per patient will also be presented using the categories (to a maximum of 6 infusions):

- < 3 infusions.
- ≥ 3 infusions.

Average volume (mL) administered per infusion will also be summarized. The duration of study drug infusion (min) will be derived as the difference between the end time and start time of study drug infusion as follows:

Duration of study drug infusion (min) = ([End time - Start time]/60 [min]).

Compliance will be derived for each patient as follows:

Compliance (%) = (Number of study drug infusions received/Number of treatment visits) x 100.

Where the number of treatment visits is counted as the number of planned treatment visits until treatment discontinuation or treatment completion (i.e. last study drug infusion expected at Week 20 of the planned treatment epoch). For patients who entered the study prior to protocol amendment 2 and were potentially treated for more than 24 weeks (more than 6 infusions), the treatment visits are counted as the number of planned treatment visits in the first 24 weeks of treatment only i.e. start of the first infusion of study drug (Day 1) to last infusion of study drug cut-off at Week 20 + 4 weeks. Infusion data recorded at or after Week 24 (EOT) will also be summarized as part of actual exposure to study drug (days) and listed in by-patient data listings.

If a patient received only part of an infusion, the patient will be regarded as having received study drug infusion at that visit for the purpose of compliance calculation.

For each patient, overall actual exposure to study drug (days) will be derived as follows:

Actual exposure (days) = ([Last infusion date + 56 days] – First infusion date) + 1 day.

The last planned infusion of study drug in terms of exposure is the Week 20 infusion per protocol amendment 2. A summary with an exposure (days) cut-off, up to a maximum of 6 potential infusions will be presented. Exposure, however, for patients entering the study prior to protocol amendment 2, may have continued beyond 24 weeks (i.e. exceeded the 6 infusions) and for this reason, actual exposure (days) will also be summarized.

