Total exposure in patient years is defined as the sum of duration of exposure (days), cut-off of all patients per treatment group and across all four treatment groups combined divided by 365.25.

The exposure to study drug (days), actual exposure to study drug (days) and total exposure in patient years, cut-off will be summarized by treatment group and across all four treatment groups combined as quantitative variables.

In addition, the number (n) and percentage (%) of patients' actual exposure to study drug, cut-off category will be presented cumulatively using the following stratification levels:

- ≥ 4 Weeks.
- ≥ 8 Weeks.
- ≥ 12 Weeks.
- ≥ 16 Weeks.
- ≥ 20 Weeks.
- ≥ 24 Weeks.

The number (n) and percentage (%) of patients assigned to the SAF analysis set (within subgroup stratification level, where relevant) with at least one study drug infusion interruption and the number of study drug infusion interruptions as recorded in the Dosage administration record – infusion eCRF will be summarized.

Reason(s) for study drug infusion interruption as recorded in the Dosage administration record – infusion eCRF categorized as:

- As per protocol.
- Adverse event.
- Lack of efficacy.
- Disease improvement under study.
- Dosing error.
- Dispensing error.
- Technical problems.
- Subject/Guardian decision.
- Physician decision.

Only one reason for study drug infusion interruption can be recorded per interruption, however patients can have multiple infusion interruptions over the course of the 24-week treatment epoch.

Premature treatment discontinuation and primary reason for premature treatment discontinuation as judged by the investigator and recorded in the Treatment epoch completion eCRF will also be tabulated by treatment group and across all four treatment groups combined.

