- Carcinogenicity: Carcinogenicity [BYM338] (CMQ) (NMQ) [narrow].
- Abuse potential: Drug abuse, dependence and withdrawal (SMQ) [broad].
- Diarrhea - Diarrhea [BYM338] (CMQ) (NMQ) [narrow].

The following actual exposure-adjusted (rate in 100 person-years) treatment-emergent AESIs regardless of study drug relationship by risk search criteria level (based on the NMQs or MedDRA SMQs) will be summarized for each treatment group and “Active Total: Safety”, overall and by region (Japan/Non-Japan) (see [Section 2.6](#) [Subgroups]). Percentages (%) will be derived relative to the number of patients “at risk” (in SAF or ongoing at the start of follow-up).

Additional data for adverse events of special interest (AESIs) related to liver, diarrhea spontaneous muscle contractions, orthopedic and heart/cardiomyopathy complications will be recorded, by the investigators, in the Liver event - overview eCRFs, Diarrhea or diarrhea-like

events eCRF, Spontaneous muscle contractions eCRF, Orthopedic complication eCRF, Heart failure eCRF and Cardiomyopathy eCRF respectively. This patient information will be summarized descriptively for all patients assigned to SAF analysis set, or who are ongoing at the start of follow-up (“at risk”).

Liver events

For treatment-emergent and post-treatment liver events, descriptive statistics (see [Section 3.2](#) [Precision and summary statistics]) will be presented based on high-level information in the Liver event – overview eCRF, Liver event - history of alcohol use 6 weeks prior to liver event eCRF and Liver event - drugs of abuse history eCRF:

- Number of treatment-emergent and post-treatment liver events (E).
- Type of liver injury:
 - Acute.
 - Acute on chronic liver disease.
 - Chronic.
- Liver failure present (yes/no).
- Tattoos in the last year (yes/no).
- Was the liver injury associated with any clinical signs/symptoms (yes/no).
- Any reasonable possibility that the liver event is related to study drug:
 - No.
 - Yes, investigational treatment.
 - Yes, other study drug (non-investigational).
 - Yes, both and/or indistinguishable.
- Did the patient discontinue study drug (yes/no).
- History of alcohol use (based on a “yes” response to the question, “Did subject use alcohol within the last 6 weeks?” on the History of alcohol use 6 weeks prior to liver event eCRF) presenting the amount of consumed alcohol (on average) by the following categories:
 - < 1 drink per day.
 - ≥ 1 to ≤ 2 drinks per day.
 - > 2 to ≤ 3 drinks per day.

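### The AESI rates per 100 person-years name an exposure that ignores the 24-week cut-off, while the events and the SAP's patient-years observe it, and the exposure formula does not stop at death or study exit

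*SAP*

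**What the plan says.** SAP 2.11.6 announces "The following actual exposure-adjusted (rate in 100 person-years) treatment-emergent AESIs regardless of study drug relationship", by treatment group, for the pooled active safety column (70, 210 and 700 mg together), overall and by region. It gives no formula for the rate.

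SAP 2.3 defines two exposures. Actual exposure covers the whole treatment duration, "i.e. disregarding the cut-off at 6 months [24 weeks] treatment". SAP 2.9.1 repeats the formula: "Actual exposure (days) = ([Last infusion date + 56 days] – First infusion date) + 1 day". The second version replaces the last infusion by "Last infusion date, within the 24-week defined treatment epoch + 56 days". SAP 2.9.1 then fixes patient-years on the second version: "Total exposure in patient years is defined as the sum of duration of exposure (days), cut-off of all patients per treatment group".

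For the events, SAP 2.3 and 2.11.1 call an AE treatment-emergent from the first infusion "until the last infusion of study drug (expected per protocol at Week 20) + 56 days". For pre-amendment 2 patients who may have had more than six infusions, SAP 2.3 says that the analysis treatment epoch "is defined as the first 24 weeks of treatment only". The footnotes to the visit-window tables in SAP 3.5.1 give their cut-off as Week 20 + 56 days.

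SAP 2.3 also applies the same definitions whether a patient completes or leaves treatment or study early, and at both the primary and the final update analysis.

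**The concern.** A rate per person-year needs one window for both parts: time belongs in the denominator only if an event in it would be counted. On the literal wording, a pre-amendment 2 patient infused beyond Week 20 adds all of that later time to the denominator, but an AESI after Week 20 + 56 days is not treatment-emergent and adds nothing to the numerator. The rate is then too low. Pre-amendment 2 patients were allocated only to placebo, 3 mg/kg (analysed as 210 mg) and 10 mg/kg (analysed as 700 mg), so the 70 mg rate is not diluted.

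A second gap affects any patient who is not followed for 56 days after the last infusion. Neither formula ends at death, withdrawal or the data cut, so time in which no event could be recorded is counted as time at risk. This error follows early exits and could differ between arms.

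**Working it through.** The documents give no AESI rate, event count or person-year total, so there is no figure to reproduce. The check is direct person-time arithmetic.

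**Inputs**
- Pre-amendment 2 patients: 14 (SAP 2.3), allocated 1:1:1 to placebo, 3 mg/kg and 10 mg/kg (Protocol 5.2). That is 14/3 = 4.67 per arm, and none in 70 mg.
- Planned arm sizes: 70, 70, 70, and 35 for 70 mg (SAP 2.13).
- Original regimen: 13 infusions over 52 weeks (Protocol, Amendment 2 summary), so the last would fall at Week 48.
- Expected 24-week completers: about 200 of 245 (Protocol 4), leaving 45.
- Assumption: days of dosing beyond Week 20 are not given. The range is one extra infusion (28 days) to seven (Week 48 − Week 20 = 28 weeks = 196 days).

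**Base person-time**
- Completer under the cut-off formula: 140 + 56 + 1 = 197 days. Counting Week 20 as study Day 140 gives 196, which changes nothing of substance.
- Arm of 70: 70 × 197 = 13,790 days = 37.75 person-years (PY). Arm of 35: 18.88 PY.

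**Uncut exposure.** Understatement = excess / (base + excess).
- 4.67 patients × 28 days = 130.7 days (0.36 PY): 130.7 / 13,920.7 = 0.9%.
- 4.67 × 196 = 914.7 days (2.50 PY): 914.7 / 14,704.7 = 6.2%.
- Five such patients, all with 13 infusions: 980 / 14,770 = 6.6% (6.7% on a 196-day base).
- Nobody dosed past the cut-off: 0%.
- 70 mg: 0% in every case.
- Pooled active column, base 175 × 197 = 34,475 days with 9.33 such patients: 261.3 / 34,736.3 = 0.8%, up to 1,829.3 / 36,304.3 = 5.0%.
- Active-versus-placebo rate ratio: unchanged with equal splits. With 5 active and 4 placebo patients at 196 extra days, it is multiplied by 14,574 / 14,770 = 0.987. With the split reversed, the factor is 1.013.
- A 210 mg or 700 mg versus 70 mg ratio carries the whole 0.9% to 6.2%.

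**Time after death or exit**
- If all 45 non-completers leave 28 days after their last dose: 45 × 28 / 365.25 = 3.4 PY unobserved, of 245 × 196 / 365.25 = 131 PY credited, or 2.6%. That base gives everyone six infusions. Shortening the non-completers' exposure raises the share to 2.7% to 3.0%.
- If none were observed after the last dose, the share is about 5.4% to 6.0%.
- Data cut at the primary analysis: if an assumed 5% to 20% of patients have only 28 of the 56 days observed, 0.05 × 28/197 = 0.7% to 0.20 × 28/197 = 2.8%.

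**The case against.** The strongest reply is that the uncut denominator is not established. SAP 2.9.1 contains the only definition of patient-years, and it uses the cut-off. The same section also attaches both the words actual and cut-off to one exposure-category variable, so the label in SAP 2.11.6 may be loose wording. This stands as a reason not to say that the rates will be understated. It does not remove the problem: a programmer following the defined term gets one denominator, and one following the patient-years rule gets another.

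A reader might infer that the 56 days are unobserved after every last infusion, which would make 56/197 = 28% of a completer's time empty. The documents do not support that. The 56 days are part of the treatment-emergent window, and AEs are collected to the last study visit (Protocol 7.1). Patients who stop treatment early return about 28 days after the last dose and again four weeks later (Protocol 5.5.9, Table 6-1 footnote), and completers are followed to Week 48. Only death, study exit or a data cut leaves credited time unobserved.

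A reader might also infer that the error flatters bimagrumab against placebo. It does not, because placebo received its share of the 14 patients.

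Two further replies stand. The data-cut part is temporary: SAP 2.4.1 says AE analyses are not final at the primary analysis, and SAP 2.4.2 updates them after Week 48. The AESI percentages and odds ratios against placebo (SAP 2.11.6, 3.11.8) do not use this denominator.

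**Conclusion.** The point holds as a conflict within the SAP, with a small and bounded numerical effect. SAP 2.11.6 names an uncut denominator, while the treatment-emergent definition and the patient-years definition observe the cut-off. If the literal wording is followed, the working above gives the effect by arm. Its upper end is a ceiling, because it needs all 13 infusions in every pre-amendment 2 patient. Protocol 5.2 sent those already beyond Week 20 to their end-of-treatment visit once Amendment 2 was implemented, so the true figure may be well below it.

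The missing truncation at death and study exit is a separate defect and applies to both exposure formulas. About 2.6% is illustrative rather than expected, since the plan schedules a visit 56 days after the last dose for early stoppers. Whether this part favours one arm depends on how early exits fall, which the documents do not tell us.

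The figures assume planned arm sizes, completer exposure as the base for the uncut-exposure figures, a near-equal split of the 14 patients, and person-time that continues after a first event. The rates are also planned by region. The region of the 14 patients is not given, so the effect there cannot be sized, but it could be larger in a small stratum.

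**What to change.** In SAP 2.11.6, replace the reference to actual exposure with an explicit definition. AESI person-time for each patient would run from the first infusion to the earliest of: last infusion within the defined 24-week treatment epoch + 56 days, death, study exit, or data cut-off. This matches the treatment-emergent window and reconciles SAP 2.11.6 with the cut-off basis of patient-years in SAP 2.9.1, adding the truncation that 2.9.1 lacks. The principle is already in use: the falls model in SAP 3.11.9 takes total days under risk as its offset. The same sentence should state whether time stops at the first event, which the SAP leaves open.

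The cost is a change of SAP wording and one derived variable from dates already collected. Total person-years become slightly smaller. Actual exposure can stay as a descriptive summary of dosing.
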